5.4 Data and Safety Monitoring Board

The appointed DSMB will plan to meet twice annually. Additional meetings will occur anytime the Board has concerns, or when requested by investigators, NIH, or regulatory authorities.

All SAEs will be reported to [name] within 24 hours of learning of the event, or [name] in the event that [name] is unavailable. Each SAE will be evaluated, and it will be determined whether it needs to be considered by the full Board.

Data will be reported using appropriate statistical techniques and tools. The reports will be generated in aggregate and split into treatment groups as defined by each protocol. All safety and efficacy data supplied for review may be blinded. Some examples of elements of a report for a protocol:

1. Patients enrolled
2. Protocol deviations
3. Selected demographic/baseline factors to include gender, race and age
4. Unexpected adverse events with resolution
5. Serious adverse events with resolution
6. Narrative reports for each serious adverse event

5.5 Follow-up for Adverse Events

Participant follow-up will be on a case-by-case basis as directed by the study physician and/or the UHCMC IRB and the DSMB as appropriate.

5.6 Specific Risks for Each Procedure

GSNO Challenge Test

We have performed GSNO challenge using this protocol in the past with no AEs (14). Theoretical risks could include hypotension, dizzy, nausea, fatigue, blurred vision, as different inhaled nitrites (such as nitroglycerine) have previously been shown to have this effect in some patients, and hemoptysis, as NO evolve from GSNO can inhibit platelet aggregation.

However, the biology of GSNO, and experience with inhaled NO and ethyl nitrite, suggests that these will not be significant complications (2,4,44,53,55). We are prepared for these if they do occur.

Bronchoscopy

Bronchoalveolar lavage and bronchoscopic brushing via flexible bronchoscopy is widely accepted as a safe procedure and is frequently utilized as a research tool in patients and healthy control volunteers (3). There is no additional risk when obtaining airway gas samples, since air is only being withdrawn. There is a slight risk of pneumothorax the vast majority of which can be treated with local manipulations but some cases may require surgical intervention.

Other risks are hemoptysis (10-25% incidence, very mild, less than 2 tablespoons in 24 h), epistaxis, local discomfort (25% incidence), fever (10-25% incidence), and sore throat. Non-specific adverse effects include acute dyspnea, cough, chest pain, and transient desaturation. There is only one report of a death resulting from a research bronchoscopy. Among those with asthma, there is a risk of transient worsening of asthma and asthma exacerbations. In the Severe Asthma Research Program experience, among the 436 participants who underwent research bronchoscopy, 5 required either unplanned hospitalization or extension of planned hospital stays for asthma exacerbations (3). Three additional participants were seen in an Emergency Room within three days of the procedure but were not treated for worsening asthma (rash, pleuritic chest pain, and panic attack). Four of the 8 participants had very severe asthma (not eligible for participation in that study).

There are specific risks and side effects from any sedative or analgesic administered as part of the bronchoscopy procedure. In addition to somnolence and reduced alertness, the participant may feel nauseous and could vomit. The drugs can induce coughing or headache. Risk of side effects is reduced by appropriately controlling rate of administration and reviewing the participant's medical history to determine if he/she has previously experienced an adverse drug event.

Fluid Collection (including Venipuncture and Urine Collection)

The risks for any type of blood sampling are bleeding, hematoma, and infection. The risk of infection is significantly reduced by the use of sterile technique. The participant may feel a stinging sensation anytime a needle is placed in the vein or artery. Also some pre- and post-procedural lightheadedness and rarely fainting may be experienced.

The genetic testing (optional) may involve social and psychological risks. Although accepted controls are in place to protect this PHI, there is always a risk that information may be unintentionally released or illegally accessed. If such an event occurred it could negatively impact the participant and their family and could also affect insurability.

Urine is self-collected using a clean catch procedure; there are no risks with this methodology.

Allergy skin testing

Possible risks include itching at the site of the skin tests, and systemic allergic reaction to the allergens tested. The allergy reactions range from mild (urticaria) to moderate (wheezing) to severe (upper airway angioedema, anaphylaxis). Medical and nursing personnel, medications and equipment will be available at the study sites to treat and manage any allergic reactions.

Standard Spirometry, maximum bronchodilator reversibility (spirometry post bronchodilator) and Fractional Exhaled Nitric Oxide (FeNO)

Such testing can cause a participant (independent of asthma status) to become light-headed, dizzy or tired. In asthmatic participants testing may also induce or worsen wheeze, shortness of breath, and/or chest tightness. Rescue therapy with Albuterol will be administered as needed. The chance of these symptoms occurring is low and treatment will be readily available. As part of the preparation for testing, a participant will be asked to withhold certain medications so an increase in allergy or asthma symptoms may occur. In such cases participants will be directed to resume their medications and the care staff may administer additional treatments and supportive therapy as warranted.

Methacholine Challenge Test (MCT)

The volunteer may experience coughing, chest tightness, shortness of breath, and/or wheezing during this procedure. These symptoms typically resolve spontaneously 10-15 minutes after testing without active intervention – recovery can be hastened as needed with administration of albuterol.

Chest x-ray

This test involves a small amount of radiation. The radiation exposure from this research is about 200 microsievert. There is radiation that naturally occurs from space and from rocks in the soil. This natural radiation is greater at higher altitudes. This research gives the same amount of radiation an individual would get from living in a high altitude city such as Denver for 12 days, or taking 4 airplane flights from New York to Los Angeles.

A possible health problem seen with radiation exposure is the development of cancer later in life. This extra cancer risk is higher at younger ages and for girls and women. The extra lifetime risk of dying of a fatal cancer due to the radiation exposure from this research may range from about one in 200,000 to about one in 70,000. At such low radiation exposures, scientists disagree about the amount of risk. These estimates are very uncertain, and there may be no extra risk at all. (These radiation estimates are from the Duke University Medical Center Radiation Safety website.)

Withholding medications

Withholding medications such as antihistamines, short-acting/long-acting bronchodilators,

antidepressants, H2 antagonists, or herbal supplements prior to study visits may cause subjects to experience increased symptoms of the condition for which the medication is taken. For example, withholding short-acting/long-acting bronchodilators might result in shortness of breath or breathing difficulty. Participants will be advised that if they experience any worsening symptoms during the pre-visit withholding period, they should use their usual medication(s) as needed and call the study team to cancel or reschedule the study visit. Participants will also receive – in the form of an addendum to the consent – a list of the medications that must be withheld, for how long prior to the study visit/testing, and possible risks associated with doing so.

Albuterol

Albuterol administration can cause nausea, vomiting, heartburn, shakiness, nervousness, dizziness, headaches, hyperactivity, and a non-harmful increase in heart rate. If such symptoms occur, they usually stop in a short period and do not require additional medications.

Viral infection testing

Viral infection testing may include collection of nasopharyngeal and/or oropharyngeal swabs. Nasopharyngeal swabs may cause mild nasal discomfort and may cause temporary mild nosebleed. Oropharyngeal. Oropharyngeal swabbing may cause mild discomfort, gagging or coughing.

6. INTERVENTION/DISCONTINUATION

A participant may be discontinued from the study at any time if the participant, the investigator feels that it is not in the participant's best interest to continue. The following is a list of possible reasons for study discontinuation:

- Participant withdrawal of consent
- Participant is not compliant with or tolerating study procedures.
- Adverse event
- Lost to follow-up
- Physician request for early termination of study
- Participant becomes pregnant

Being a part of this study while pregnant may expose the unborn child to significant risks. Therefore, pregnant women will be excluded from the study. A pregnancy test will be done at the beginning at every study visit for any women of childbearing potential, and it must be negative before they can enter and continue in this study. All Participants must agree to use appropriate contraceptive measures during the study. Medically acceptable contraceptives include: (1) surgical sterilization, (2) approved hormonal contraceptives such as birth control pills, (3) barrier methods (such as a condom or diaphragm) used with a spermicide, or (4) an intrauterine device (IUD). If they become pregnant during this study, they must inform a member of the research team immediately.

All participants are free to withdraw from participation at any time, for any reason, specified or unspecified, and without prejudice. If the participant withdraws from the study and also withdraws consent for disclosure of future information, no further evaluations should be performed, and no additional data should be collected.

The Investigator may retain and continue to use any data collected before such withdrawal of consent. Any samples already being analyzed will be completed and any stored samples will be destroyed if still linkable.

7. STATISTICAL CONSIDERATIONS

7.1 Statistical Analysis of Outcomes and Power Calculations

Based on our preliminary data, we project 44% (n=22) of the 50 participants we enroll with asthma will have elevated GSNOR activity in BAL fluid ($> 7.5 \text{ mmole} \times \text{min}^{-1} \times \text{ug protein}^{-1}$) compared with approximately 15% of healthy volunteers (16). Levels of tissue GSNOR expression will be log-transformed to improve normality assumptions. Values will be compared between those with and without elevated GSNOR in BAL fluid using a two-sample t-test or Wilcoxon rank sum test if normality assumptions are not met. Inter-relationships will be assessed using Pearson or Spearman's correlation. Assuming lognormal distributions and a coefficient of variation of 50%, this study will have $\geq 83\%$ power to detect a 1.5-fold or larger differences between groups. Correlations between BAL enzyme activity and GSNOR expression levels of 0.39 or higher can be detected with 80% power. These and other power and sample size calculations assume two-sided tests with significance taken at $p < 0.05$.

To test the hypothesis that the GSNO challenge test can reliably identify those with elevated GSNOR activity levels, the primary outcome will be the amount that FeNO declines from its observed maximum to its value 15 minutes post-exposure. There will be three cohorts: asthma participants with abnormal GSNOR ($> 7.5 \text{ mmole} \times \text{min}^{-1} \times \text{ug protein}$), asthma participants with normal GSNOR, and ten non-asthmatic healthy controls. One-way ANOVA or Kruskal-Wallis tests be used to primary outcome among cohorts, possibly after log-transformation. If approximate normality of the outcome cannot be achieved with or without transformation, Kruskal-Wallis/Wilcoxon rank sum tests will be used. In addition, a linear mixed repeated-measures model will be used to estimate and compare FeNO vs. time profiles of the three cohorts. Assuming lognormal distributions, a coefficient of variation of 50%, and sample sizes of 22 asthma participants with elevated GSNOR, 28 asthma participants with normal GSNOR, and 10 healthy normal participants, the study will have $\geq 80\%$ power to detect 1.5-fold or larger differences between the increased GSNOR phenotype and non-increased phenotype asthmatics, or to detect a 1.7 fold difference between the increased GSNOR phenotype and the non-asthmatic control participants. Correlations between amount of FeNO decline from the maximum in 15 min, or maximal increase in FeNO and BAL GSNOR levels of 0.39 or higher can be detected with 80% power.

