2. STUDY OBJECTIVES AND HYPOTHESES

2.1 Primary Objectives

- 2.1.1 To validate and characterize the increased S-nitrosogluthathione reductase (GSNOR) phenotype in asthma by measuring enzyme expression and activity in bronchoscopic biopsies from adult asthmatics and healthy volunteers. We will corroborate our previous airway GSNOR activity data in participants with asthma across the spectrum of severity to confirm that the phenotypic features are relevant to asthma, and to have a validated GSNOR measure against which to compare the results of the GSNO challenge test in the same patients.
- 2.1.2 To validate non-invasive methodology to identify participants with asthma who have elevated airway GSNOR activity using inhaled GSNO challenge followed by test the hypothesis that inhaled GSNO challenge followed by Fractional Exhaled Nitric Oxide (FeNO) measurements will confirm the diagnosis of increased GSNOR activity in the airways of patients with SA. We will use FeNO as a measure of inflammatory biochemistry. This will provide a diagnostic test for patients suspected clinically of enhanced GSNOR activity.

[figure not shown]

Figure 2. A. Activity of S-nitrosogluthathione reductase (GSNOR) in bronchoalveolar lavage (BAL) fluid was significantly higher in subjects with asthma compared with healthy volunteers (p=0.03). B. GSNOR activity was also higher in BAL cell lysates from subjects with asthma compared with healthy volunteers (p=0.02). C. Regression analysis showed a significant association between the concentration of methacholine that provoked a 20% decrease in FEV₁ (PC₂₀) and BAL cell lysate GSNOR activity in subjects with asthma.

[figure not shown]

Figure 3. S-nitrosogluthathione reductase (GSNOR) activity levels in the bronchoalveolar lavage (BAL) cell lysate fluid was higher in subjects with non-severe and severe asthma compared with controls, but showed variability that was not associated with asthma severity.

If bronchoscopies cannot be consistently performed due to viral infection crisis regulations, the primary objective will be:

2.1.1.1 Measure the AUC difference in FeNO over time after inhalation of GSNO between patients with disease and those without.

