2.2 Hypotheses

2.2.1 Elevated GSNOR activity ($> 7.5 \text{ mmol} \times \text{min}^{-1} \times \text{ug protein}^{-1}$) will be present in approximately 40% of participants with asthma irrespective of asthma severity compared with $<10\%$ of healthy volunteers.

2.2.2 Participants with asthma who have elevated airway GSNOR activity can be reliably identified by their FeNO profile after inhaled GSNO challenge.

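### The claim that the GSNO challenge reliably identifies elevated GSNOR is tested only by group differences and correlations, which do not estimate how well individual patients are classified

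*Combined protocol and SAP*

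**What the plan says.** The question is posed at the level of the individual patient. Hypothesis 2.2.2 reads: "Participants with asthma who have elevated airway GSNOR activity can be reliably identified by their FeNO profile after inhaled GSNO challenge". Objective 2.1.2, listed as primary, aims to validate a non-invasive method and adds: "This will provide a diagnostic test for patients suspected clinically of enhanced GSNOR activity". The reference standard is BAL GSNOR activity above or below 7.5, and Section 3 blinds the staff who run the challenge to the bronchoscopy results.

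Section 7.1 introduces the analysis with the words "To test the hypothesis that the GSNO challenge test can reliably identify those with elevated GSNOR activity levels" and defines the endpoint for this hypothesis: "the primary outcome will be the amount that FeNO declines from its observed maximum to its value 15 minutes post-exposure". The analyses are:

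- the cohort comparison: "One-way ANOVA or Kruskal-Wallis tests be used to primary outcome among cohorts, possibly after log-transformation", with rank tests (Kruskal-Wallis, Wilcoxon rank sum) if normality fails. The cohorts are asthma with elevated GSNOR, asthma with normal GSNOR, and ten healthy controls;
- "a linear mixed repeated-measures model will be used to estimate and compare FeNO vs. time profiles of the three cohorts";
- correlations of FeNO decline, or of maximal FeNO rise, with BAL GSNOR.

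Power is stated as at least 80% for a 1.5-fold or larger difference between the two asthma cohorts and for a 1.7-fold difference between elevated-GSNOR asthma and healthy controls, and as 80% for a correlation of 0.39.

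No FeNO cut-off, ROC curve, sensitivity, specificity, predictive value or accuracy target appears in the document. The 7.5 threshold applies to the BAL reference measure only.

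**The concern.** A difference between groups and a usable diagnostic test are different things. Two cohorts can differ clearly on average while their distributions overlap so much that no cut-off sorts individuals well. A significant cohort comparison shows that the FeNO measure carries some information about GSNOR status. The rank test between the two asthma cohorts, for instance, has AUC = 0.5 as its null, so rejecting it means better than chance. It does not mean reliable.

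The three-cohort test has a second weakness. It can be significant because healthy controls differ from asthma, even if the two asthma cohorts are alike. Only the within-asthma contrast bears on hypothesis 2.2.2, and the plan does not name it as the deciding one.

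At stake is the study's central claim. A p-value below 0.05 could be reported as validation of a diagnostic test without any estimate of how often the test is wrong.

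**Working it through.** **Inputs (Section 7.1).** Lognormal outcome, CV 50%; 22 elevated and 28 normal asthma participants, 10 healthy; 1.5-fold and 1.7-fold effects; r = 0.39; two-sided 0.05; projected prevalence of elevated GSNOR in asthma 44%.

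**Step 1: reproduce the plan's power.**

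- Log-scale SD: σ = √ln(1 + 0.5²) = √ln 1.25 = 0.472.
- 1.5-fold, 22 vs 28: noncentrality = ln 1.5 / (0.472 × √(1/22 + 1/28)) = 0.405 / (0.472 × 0.285) = 3.01; two-sample t-test power 83.9%.
- 1.7-fold, 22 vs 10: power 81.3%.
- r = 0.39, n = 50, Fisher z: power 80.6%.

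All three agree with the stated figures, so what follows uses the plan's own model.

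**Step 2: translate the effect into accuracy.** Added assumptions: equal log variances, one marker, cut-off midway between the log means. With d = ln(fold)/σ, AUC = Φ(d/√2), sensitivity = specificity = Φ(d/2), and the misclassified share is Φ(−d/2).

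At 1.5-fold:

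- d = 0.405/0.472 = 0.858; AUC = Φ(0.607) = 0.73.
- Sensitivity = specificity = Φ(0.429) = 66.6%; misclassified 33.4%. The best cut-off at 44% prevalence still misclassifies 32.8%.
- PPV = 0.44 × 0.666 / (0.44 × 0.666 + 0.56 × 0.334) = 61%; NPV 72%.
- With sensitivity held at 90%, specificity is 34%.

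**Step 3: the smallest significant result.** Critical t on 48 df = 2.011, so d = 2.011 × 0.285 = 0.573 and the ratio is exp(0.573 × 0.472) = 1.31. AUC = Φ(0.405) = 0.66; misclassified Φ(−0.286) = 38.7%.

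**Step 4: other true effects.**

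| Fold difference | AUC | Misclassified |
|---|---|---|
| 1.31 (just significant) | 0.66 | 39% |
| 1.5 (powered) | 0.73 | 33% |
| 2 | 0.85 | 23% |
| 3 | 0.95 | 12% |

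Sensitivity = specificity of 80% needs about 2.2-fold; 90% needs about 3.4-fold.

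**Step 5: dependence on the CV at 1.5-fold (range assumed).** CV 40% gives 30% misclassified and CV 60% gives 36%. Taking 0.50 as the log SD gives 34%.

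**Step 6: the omnibus test.** Suppose the two asthma cohorts are identical and only healthy controls differ, by 1.7-fold. The noncentrality is (10 × 50/60) × (0.531/0.472)² = 10.5, and the F test on 2 and 57 df is significant about 81% of the time, with no discrimination within asthma.

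**Step 7: precision if accuracy is the target.** The Hanley-McNeil SE at AUC 0.85 with 22/28 is 0.058, so the 95% half-width is 1.96 × 0.058 = 0.11. Exact 95% intervals for illustrative counts: 18/22 (82%) gives 60% to 95%; 25/28 (89%) gives 72% to 98%.

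**The case against.** The plan is broader than a comparison of means. It provides rank tests, and the Wilcoxon statistic is a rescaled AUC. It models whole FeNO profiles and correlates FeNO response with BAL GSNOR as a continuous variable. It powers the two asthma cohorts against each other separately, so the within-asthma contrast is clearly contemplated. Section 9.1 describes the aim as determining a relationship, which a correlation does address, and Section 9.6 says results will not guide clinical care.

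Much of this stands. It would be wrong to say that the plan looks only at means or ignores the within-asthma contrast; the fair criticism is that no contrast is named as decisive. But these analyses still measure association. Turning an estimated group difference into classification accuracy requires a further step that the plan does not contain.

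A reader might also infer that the test will misclassify one patient in three. The documents do not support that. The 1.5-fold figure is the smallest effect the study is powered to detect, stated as 1.5-fold or larger, and is not an expected result. Hypothesis 2.2.2 also concerns the FeNO profile, and Section 3 names baseline, rate of rise and duration, so accuracy of the profile need not equal that of a single marker.

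Finally, one might insist on a pass/fail rule for the lower AUC limit. That is a real trade-off. At a true AUC of 0.85 and SE 0.058, the lower 95% limit would clear assumed thresholds of 0.70, 0.75 and 0.80 about 74%, 41% and 14% of the time (normal approximation, fixed SE).

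**Conclusion.** The concern holds in this form: the plan poses an individual-level diagnostic question and tests it with group comparisons and correlations, none of which estimates individual classification. It also leaves open which contrast decides the hypothesis. A significant result would be compatible with AUC 0.66 and about 39% misclassified (ratio 1.31), with AUC 0.73 and about 33% (1.5-fold), or with something much better (12% at 3-fold), and the significance test does not tell these apart.

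The figures rest on the plan's lognormal model with CV 50%, and on equal log variances, a single marker and a midpoint cut-off. They show what significance is compatible with and do not forecast how the test will perform.

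**What to change.** For objective 2.1.2, before any analysis:

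- Make the main analysis the ROC AUC with 95% CI of one prespecified FeNO measure, for elevated versus normal BAL GSNOR, in asthma participants with BAL data only. Call it the ROC AUC throughout, because contingency objective 2.1.1.1 uses AUC for the FeNO-time curve. Define the measure on the scheduled readings: FeNO is taken every 10 minutes, while the endpoint refers to a 15-minute value.
- Report sensitivity and specificity with exact CIs at a stated cut-off. If the cut-off is derived from these data, correct for optimism by bootstrap or cross-validation.
- Name elevated versus normal GSNOR within asthma as the deciding contrast. Keep the three-cohort test, mixed model and correlations as supportive.
- Base any statement that the test reliably identifies patients or is validated on the ROC AUC and its interval, not on a group-difference p-value. A formal AUC threshold is optional and would need its own power statement.

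The cost is analysis-plan text and modest extra computation; BAL GSNOR and serial FeNO are already scheduled. The downside is a wide interval: about ±0.11 at AUC 0.85 with 22/28, and wider if participants opt out of bronchoscopy as Section 4.6 allows during crisis restrictions. The diagnostic claim may then have to be softened.

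### The primary outcome is tested across three cohorts, but the stated power is for two-group comparisons, and a significant three-cohort result need not show that the challenge separates elevated- from normal-GSNOR asthma

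*Combined protocol and SAP*

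**What the plan says.** Section 7.1 of the combined protocol and SAP defines the outcome for the challenge test: "the primary outcome will be the amount that FeNO declines from its observed maximum to its value 15 minutes post-exposure". It sets up three cohorts (asthma with elevated GSNOR, asthma with normal GSNOR, healthy controls) and names the test: "One-way ANOVA or Kruskal-Wallis tests be used to primary outcome among cohorts, possibly after log-transformation". The fallback is: "If approximate normality of the outcome cannot be achieved with or without transformation, Kruskal-Wallis/Wilcoxon rank sum tests will be used".

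The power statement that follows assumes lognormal data, a CV of 50% and group sizes of "22 asthma participants with elevated GSNOR, 28 asthma participants with normal GSNOR, and 10 healthy normal participants". It claims at least 80% "power to detect 1.5-fold or larger differences between the increased GSNOR phenotype and non-increased phenotype asthmatics". The same figure is claimed for a second comparison, elevated-GSNOR asthma against healthy controls, at 1.7-fold. Significance is two-sided at 0.05.

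The section gives no power for the three-cohort test and no assumed healthy-control mean. It does not name a pairwise contrast as primary, say whether the omnibus test must be significant before pairwise testing, or give a multiplicity rule. Hypothesis 2.2.2 in section 2.2 is about recognising elevated airway GSNOR activity among participants with asthma.

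**The concern.** The test that is named and the power that is quoted belong to different comparisons. This matters in two ways.

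First, the power of a three-group test for a fixed difference between the asthma cohorts varies with where the third group falls. The quoted figure therefore does not carry over to the omnibus test.

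Second, the omnibus null hypothesis is that all three means are equal. Rejecting it does not say which cohorts differ. A shift in the 10 healthy controls alone can produce a significant primary result, and that says nothing about whether the challenge separates the two asthma phenotypes. A reader of the final report could then take a positive primary test as support for the diagnostic claim when the data do not bear on it.

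**Working it through.** **Inputs (section 7.1).** Group sizes 22 / 28 / 10; CV 50%, lognormal; two-sided 0.05; 1.5-fold between the asthma cohorts; 1.7-fold between elevated-GSNOR asthma and healthy controls. The healthy mean relative to normal-GSNOR asthma is not given, so it is varied.

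**Log-scale SD.** σ = √ln(1 + 0.5²) = √0.2231 = 0.472. Also ln 1.5 = 0.405 and ln 1.7 = 0.531.

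**Step 1: reproduce the plan's figure.** For a two-sample t-test, the noncentrality is δ = ln(ratio) / [σ√(1/n₁ + 1/n₂)].
- 22 vs 28, 1.5-fold: δ = 0.405 / (0.472 × √(1/22 + 1/28)) = 3.01; power 83.9% (48 df).
- 22 vs 10, 1.7-fold: δ = 0.531 / (0.472 × √(1/22 + 1/10)) = 2.95; power 81.3% (30 df).

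Both agree with the stated 80% or more, at an unadjusted 0.05. The quoted power is that of two-group tests.

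**Step 2: power of the three-cohort ANOVA for the same 1.5-fold asthma difference.** Noncentral F with 2 and 57 df and λ = Σnᵢ(μᵢ − μ̄)²/σ². Put normal-GSNOR asthma at 0, elevated at L = 0.405 and healthy at c. Then

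λ = [(22×28/50)L² + (50×10/60)(c − 0.44L)²] / σ².

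The first term alone is 12.32 × 0.1644 / 0.2231 = 9.08. It is the minimum, reached when healthy controls sit at the weighted mean of the two asthma cohorts (c = 0.44L, ratio about 1.20).

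| Healthy mean relative to normal-GSNOR asthma | λ | Omnibus power |
|---|---|---|
| 0.88 (1.7-fold below elevated) | 12.52 | 88.0% |
| 1.00 (equal to normal-GSNOR asthma) | 10.27 | 80.4% |
| 1.04 | 9.79 | 78.4% |
| 1.06 | 9.59 | 77.5% |
| 1.20 (least favourable) | 9.08 | 75.1% |
| 1.50 (equal to elevated-GSNOR asthma) | 11.00 | 83.2% |

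Power is below 80% for ratios of about 1.01 to 1.42. The 1.04 and 1.06 rows arise if the response follows GSNOR status alone and 10% or 15% of healthy volunteers are elevated. Section 2.2 expects fewer than 10% and section 7.1 about 15%; the normal-GSNOR asthma cohort has none by definition.

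Simulated Kruskal-Wallis power (6,000 runs) is about 73% at the least favourable mean and 78% if healthy equal normal-GSNOR asthma. The direct Wilcoxon comparison of the asthma cohorts gives about 81–82%.

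**Step 3: significance driven by healthy controls alone.** Set the two asthma means equal and place healthy controls 1.7-fold away. Then λ = (50×10/60) × 0.531² / 0.2231 = 10.5, and the omnibus F test is significant with probability 81%.

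**Step 4: the direct contrast.** A prespecified elevated-versus-normal contrast has 83.9% power as a t-test, or 84.2% inside the ANOVA (57 df). Neither depends on the healthy mean.

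**The case against.** A reader might infer from the table that the study is underpowered at about 75%. The documents do not support that. The figure needs a healthy mean between the two asthma cohorts, at about 1.2 times normal-GSNOR asthma, and nothing in the plan places it there. If the plan's two detectable differences held together in the same direction, omnibus power would be 88%, above the claim. Even requiring both the omnibus F test and the pairwise t-test to be significant would give about 81%. In turn, the 1.7-fold figure may be only what 22 versus 10 can detect, not an expected mean, so 88% is not established either.

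A second tempting reading is that the plan makes the omnibus test a gate. It does not say so. The section speaks of the study's power for two named differences and mentions the Wilcoxon rank sum test, so pairwise comparisons were evidently in mind. An ANOVA with a prespecified contrast would be a normal way to proceed and would keep 84.2%.

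Nor is the omnibus test the only evidence on 2.2.2. The section also plans a mixed model of FeNO profiles and a correlation of FeNO decline with BAL GSNOR.

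What remains is that no contrast is actually prespecified. Wilcoxon appears only in the non-normal fallback, and the mixed model and correlation are additional analyses. The inference problem in step 3 does not depend on any view about power.

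**Conclusion.** The point holds as a mismatch between the primary test, the quoted power and the hypothesis. The stated power is correct for two-group comparisons but is not given for the test named. For a 1.5-fold asthma difference, ANOVA omnibus power runs from 88% through 80% to a worst case of 75% in the placements examined, and is about 78% if healthy controls sit slightly above normal-GSNOR asthma. At most this is 5 points under the stated 80%, and in some placements there is no shortfall.

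The more serious consequence is interpretive. The omnibus test has an 81% chance of significance when only healthy controls differ, by 1.7-fold, so its success need not bear on hypothesis 2.2.2.

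These results assume the plan's CV of 50%, lognormal data with a common log-scale SD, and all 60 participants contributing at 22/28/10. Missing bronchoscopy data and dropout are not included.

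**What to change.** In section 7.1, name elevated- versus normal-GSNOR asthma as the single primary test: log scale, two-sided 0.05, by t-test or ANOVA contrast, or by Wilcoxon if normality fails. State that it is not conditional on the omnibus test. The existing claim of at least 80% power for a 1.5-fold difference then describes the primary test, at about 84% by t-test.

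Make the three-cohort test and the healthy-control contrasts secondary. Either test them only after the primary contrast is significant, or report them without a confirmatory claim. A rule is needed: if the two pairwise contrasts instead shared alpha at 0.025 each, power for the 1.5-fold contrast would drop to about 76%.

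If the omnibus test stays primary, state its power with assumed means for all three cohorts instead of the pairwise figure, and say how the asthma contrast will be read after it.

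The cost is a sentence or two of text and no additional participants, visits or data. The downside is that the comparison with healthy controls becomes secondary.
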